7.4.2 Skeletal Survey or WBLT-CT

X-ray skeletal survey or whole-body low-dose CT (WBLD-CT) is required for screening and thereafter as per the Time and Events Table.

7.5 Patient Reported Outcomes/Quality of Life

7.5.1 CARG Global Assessment

The CARG-GA assesses various domains including functional status, social determinants of health, and falls, among others. The GA will be administered either in person or online. Information on how subjects will complete the assessment will be provided to sites.

Note that there is a coordinator-completed component and a subject-completed component to the GA. Coordinators complete the same form with each assessment (Appendix I. CARG Global Assessment: Healthcare Team). For subjects, the first time they complete the GA they should complete the **baseline** assessment (Appendix J. CARG Global Assessment: Subject-Completed Baseline Questionnaire). Subsequent assessments should be completed using the **subsequent** assessment form (Appendix K. CARG Global Assessment: Subsequent Assessment).

7.5.2 IMWG Frailty

The IMWG Frailty assessment tool requires the following assessments:

- Charlson Comorbidity Index
- Katz Activities of Daily Living (ADL)
- Lawton Instrumental Activities of Daily Living (iADL)

Appendix C. Instructions for Scoring IMWG Frailty Assessment Tool, Including Lawton IADL and Katz ADL Assessments and Charlson Comorbidity Index provides additional information.

7.5.3 Q-TWiST

Quality-adjusted Time Without Symptoms of disease progression or Toxicity of treatment (Q-TwiST) assesses the time without symptoms or toxicity. Toxicity, time without toxicity and relapse will be captured throughout the study.

7.5.4 EORTC QLQ-C30

The tool assesses the quality of life in individuals with cancer. This will be provided to sites as a PDF and/or electronically (Appendix D. EORTC QLQ-C30).

7.5.5 EORTC QLQ-MY20

The tool assesses the quality of life in individuals with multiple myeloma. This will be provided to sites as a PDF and/or electronically (Appendix E. EORTC-MY20).

7.5.6 Mini-Cog and PROMIS-cog

Mini-Cog and PROMIS-cog (Appendix H. Mini-Cog and Appendix G. PROMIS Cognitive Function-Short Form 8a) are validated instruments for assessing cognitive and subjective cognitive impairment, respectively. Coordinators administering Mini-Cog will be trained in how to administer the test. Forms will be provided to sites.

7.5.7 Gait Speed

Gait speed will be evaluated as part of the CARG-GA and is found in Appendix L. Gait Speed.

7.5.8 Financial Toxicity

Financial toxicity will be evaluated using the COST-FACIT questionnaire, which will be provided to sites (Appendix F. COST-FACIT).

7.6 Correlative Studies

Bone marrow biopsy/aspirate should be obtained per the Time and Events Table in section 8.1. Specimens will be collected for correlative research (non-UNC multicenter sites may opt-out of this component of the study) only at the screening and EOT timepoints.

Blood draws will be performed per the Time and Events Table in section 8.1. Blood biomarker sample collection (non-UNC multicenter sites may opt-out of this portion of the study) is performed at C1D1, C4D1, and at end-of-treatment.

For UNC subjects (mandatory) and non-UNC multicenter sites (unless opted-out of this component of the study) we will evaluate immune cell populations in the bone marrow and peripheral blood as justified in 1.8.2. We will also study peripheral blood T-cell *p16^{INK4}* levels as discussed in section 1.8.1.

Please refer to the laboratory manual for details on sample collection.

8.0 EVALUATIONS AND ASSESSMENTS

8.1 Time and Events Table

Assessment	Screening ^{1c}	C1 D1 ²	C1 D8 ²	C1 D15 ₂	C1 D22 ²	C2 D1 ²	C2 D15 ²	C3 D1 ²	C3 D15 ²	C4+ D1 ²	C4+ D15 ²	EOT ³	Post- Treatment Visits ³ (Study)	Long- term Follow- up ³
Informed Consent	X													
Eligibility Verification	X													
Medical history	X ^{1a}	X				X		X		X		X	X	X
Physical exam	X ^{1a}	X				X		X		X		X	X	
Vital signs	X ^{1a}	X	X	X	X	X	X	X		X		X	X	
Karnofsky Performance Status	X	X				X		X		X		X	X	
Serum Pregnancy Test and Contraception Screening ^{1d, 1e}	X	X	X	X	X	X	X ^{1d}	X	X ^{1d}	X	X ^{1d}	X ^{1d}		
Skeletal Survey or WBLD-CT	X ^{1a}	As clinically indicated										X		
Plasmacytoma evaluation ¹⁰	X ^{1a}	As clinically indicated										X		
Bone marrow aspiration/biopsy ⁷	X ^{1b}	As clinically indicated										X		
Hematology ⁴	X ^{1c}	X	X	X	X	X	X	X				X	X	
Type and screen, red blood cell phenotyping (prior to isatuximab)		X												
Serum Chemistry ⁵	X ^{1c}	X	X	X	X	X	X	X		X		X	X	

Assessment	Screening ^{1c}	C1 D1 ²	C1 D8 ²	C1 D15 ₂ ²	C1 D22 ²	C2 D1 ²	C2 D15 ²	C3 D1 ²	C3 D15 ²	C4+ D1 ²	C4+ D15 ²	EOT ³	Post- Treatment Visits ³ (Study)	Long- term Follow- up ³
β-2-microglobulin and LDH	X	X										X		
M-protein quantification ⁶ and serum free light chain assay	X	X				X		X		X		X	X	
Blood biomarker collection ⁸		X ⁸								X ⁸		X ⁸	X ⁸	
Isatuximab IV		X	X	X	X	X	X	X	X	X	X			
Pomalidomide PO ¹²		X ¹²												
Dexamethasone PO ⁹		X	X	X	X	X ⁹								
Subject Pill Diary ¹⁴		X				X		X		X				
Clinical toxicity assessment (CTCAE v5.0) ¹¹	X	X	X	X	X	X	X	X	X ¹¹	X ¹¹	X ¹¹	X	X	
Concomitant medications review	X	X	X	X	X	X		X		X		X		
CARG-Global Assessment	X ⁸									X ⁸		X ⁸	X ⁸	
Gait speed test, PROMIS-cog, Mini-cog, ¹³	X ¹³									X ¹³		X ¹³	X ¹³	
IMWG Frailty assessment	X ⁸													
EORTC QLQ-C30, EORTC QLQ-MY20 QOL assessments ⁸		X ⁸								X ⁸		X ⁸	X ⁸	
Survival														X

Footnotes to Time and Events Table

1. Screening Windows for assessments are as follows:

- a. Complete history, physical exam and all imaging assessments should be performed within 21 days prior to day 1 of study treatment in cycle 1 except x-ray skeletal survey or WBLD-CT scan, which may be performed up to 4 weeks prior to cycle 1 day 1.
 - b. Baseline bone marrow biopsy/aspirate should be obtained within 4 weeks prior starting treatment on cycle 1 day 1.
 - c. All screening evaluations (except for pregnancy test) must be performed within 21 days prior to cycle 1 day 1 unless otherwise stipulated. Screening hematology and chemistry labs must be completed within 72 hours prior to start of treatment on Day 1, Cycle 1. All lab testing and study visits may be performed up to 24 hours prior to isatuximab infusion if clinically appropriate, for subject convenience.
 - d. Serum β -HCG pregnancy test must be performed within 10-14 days of cycle 1 day 1 and then again within 24 hours of cycle 1 day 1 for women of child-bearing potential. Additional pregnancy tests are required weekly during first 4 weeks of therapy and then on a monthly basis thereafter in subjects with regular menstrual cycles or every two weeks if the menstrual cycle is irregular. Additional pregnancy tests will be required if a menstrual cycle is missed or there is unusual menstrual bleeding, or if pomalidomide is not dispensed within 7 days of taking the pregnancy test.
 - e. Men must agree to use a latex or synthetic condom during sexual contact with a FCBP even if they have had a vasectomy from the time of signing the informed consent form through 90 days after the last dose of pomalidomide and 5 months after the last dose of isatuximab. These same patients must not donate sperm. All patients must be counseled at a minimum of every 28 days about pregnancy precautions and risks of fetal exposure. All patients enrolled into this trial, must be registered in and must comply with all requirements of the POMALYST REMS program.
2. A window of ± 3 days applies to all study visits unless otherwise specified. Study visit including all lab testing may be performed up to 1-day prior to isatuximab infusion, if clinically appropriate, for subject and clinic convenience. If screening medical history and physical exam are performed within 3-days of C1D1, these do not need to be repeated on C1D1.
 3. The end of treatment visit should only occur when subjects permanently stop study treatment and should be performed within 30 days (± 7 days) after the last dose of study medication. Subjects will be followed for adverse events during this 30-day period.

Post-treatment visits will be conducted for subjects who have an ongoing \geq grade 3 or serious AE (SAE) at the end of treatment visit and will be continued until the event is resolved or deemed irreversible by the investigator. These visits will occur at least once every 4 weeks (± 1 week) for the first 6 visits and then once every 12 weeks (± 2 weeks) thereafter. However, follow-up every 12 weeks by telephone or any other modality is permissible if a less frequent monitoring schedule is clinically appropriate, and if the subject would otherwise require removal from the study.

In addition, post-treatment visits will be conducted for subjects who remain progression free at their end of treatment visit and will occur once every 4 weeks (± 1 week) for the first 6 visits and then once every 12 weeks (± 2 weeks) thereafter until disease progression or the start of a new MM treatment. If follow up of \geq grade 3 or serious adverse events (as outlined above) has also concluded, patients will then enter the long-term follow-up phase. If possible, during the post-treatment phase, subjects should complete the Karnofsky performance status, CARG global assessment, quality of life assessment, cognitive testing, and blood correlatives every six months until they enter the long-term follow up phase.

The Long-Term Follow-up period will begin (except in the case of withdrawal of consent) after the end of treatment and post-treatment (if applicable as outlined above) visits and will take place every 3 months

(±2 weeks) for a maximum of 3-years from the end-of-treatment visit. Long-Term Follow-up visits will be limited to history of any subsequent cancer treatments, diagnosis of another cancer and survival status. Long-term follow up assessments may be conducted either in person, by telephone, via audio/video, medical record abstraction, or by other modality deemed appropriate for this purpose by the investigator.

After documented progression of MM and/or initiation of other, non-study therapy, follow-up should be every three months by any modality (telephone, via audio/video, or by other modality deemed appropriate for this purpose by the investigator).

4. Hematology: CBC with white blood cell differential

5. Serum chemistries must include the following:

- Every chemistry assessment: sodium, potassium, chloride, CO₂, BUN, creatinine, glucose, and calcium.
- Day 1 of each cycle only: also include albumin, total protein, total bilirubin, AST, ALT, alkaline phosphatase.

6. SPEP, serum IFE, serum immunoglobulin quantification (IgG, IgA, IgM, plus IgD and/or IgE if clinically indicated for IgD or IgE myeloma) and 24h UPEP/IFE. Sebia Hydrashift ISA assay (Labcorp) is recommended for patients with IgG-kappa multiple myeloma in VGPR or better.

7. For morphology, flow cytometry, conventional cytogenetics, FISH, and correlative assessment (unless non-UNC multicenter site that has opted-out of the correlative portion of the study). MRD testing by next generation sequencing with minimum sensitivity of 1×10^{-5} by next generation sequencing should be performed if subject appears to be in complete response by serum and/or urine markers.

BM biopsy should be repeated every 12 weeks in subjects with non-secretory disease.

8. IMWG Frailty Assessment is only performed at screening, using CARG-GA administered at screening. CARG-GA is then again assessed at C4D1, at D1 of every 3rd cycle thereafter (C7, C10, etc.), at EOT, and every six months (during post-treatment visits) until progression of MM and/or initiation of other MM therapy.

Regarding CARG-GA, there is a coordinator-completed component and a subject-completed component to the GA. Coordinators complete the same form with each assessment ([Appendix I](#)). For subjects, the first time they complete the GA they should complete the **baseline** assessment ([Appendix J](#)). Subsequent assessments should be completed using the **subsequent** assessment form ([Appendix K](#)).

IMWG frailty assessment should be completed using the scoring instructions in [Appendix C](#).

EORTC QLQ-C30, EORTC QLQ-MY20 QOL assessments are performed at C1D1 (or during screening), C4D1, at D1 of every 3rd cycle thereafter (C7, C10, etc.), at EOT, and every six months (during post-treatment visits) until progression of MM and/or initiation of other MM therapy.

Blood biomarker sample collection (non-UNC multicenter sites may opt-out of this portion of the study) is performed at C1D1, C4D1, and at end-of-treatment.

9. Dexamethasone is given on days 1, 8, 15 and 22 of each cycle. On days that both dexamethasone and isatuximab are given, dexamethasone should be administered prior to isatuximab infusion on days patient receives isatuximab. Note: Dexamethasone should be given with a snack/light meal to reduce gastric irritation.

10. CT, MRI or PET-CT should be performed with screening if a subject is known to have an extramedullary plasmacytoma. If done, the same technique should be employed as clinically indicated during the study treatment (including if relevant to confirm response), and again at the end of study treatment.
11. From Cycle 3 and beyond, assess toxicity at D1 of each cycle and as needed.
12. Administered daily on Days 1-21 of a 28-day cycle
13. Gait speed ([Appendix L](#)), PROMIS-cog ([Appendix G](#)) and Mini-Cog ([Appendix H](#)) testing cannot be performed virtually, rather must be performed in-person. Prior to starting study treatment, subject may complete these items either up to 21 days prior to cycle 1 day 1 OR on cycle 1 day 1 itself, whichever is more convenient for an in-person encounter with a study coordinator. For subsequent assessments, if subject is scheduled for these tests but conducting a virtual visit that day, then these assessments should be postponed until next in-person visit. It has been <2 months since these tests were last conducted, these items can be skipped to avoid redundancy.
14. Pill diary should be checked for subject adherence at the beginning of every cycle.

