- ii) History of requiring dose-reduction of at least two separate anticancer drugs during prior therapy for multiple myeloma.

Subjects qualifying for enrollment by criteria (C) should be discussed with study PI before enrollment, to ensure uniform application of this criterion across participating sites.

4.1.8 Measurable disease as defined by one or more of the following:

- A. Monoclonal protein (M-protein) present in serum and/or urine, defined as serum M-protein of ≥ 0.5 g/dL
- B. Urine M-protein of ≥ 200 mg/24 hours
- C. Involved light chain ≥ 10 mg/dL (100 mg/L) AND abnormal serum free light chain ratio.

Subjects without measurable disease (including non-secretory multiple myeloma) will also be eligible to participate if the baseline marrow burden of myeloma is at least 30%.

4.1.9 Subjects who require radiotherapy (which must be localized in its field size) may be enrolled but initiation of study therapy should be deferred until the radiotherapy is completed and 14 days have elapsed since the last date of radiotherapy.

4.1.10 Demonstrate adequate organ function as defined in the table below; all screening labs to be obtained within 72 hours prior to initiating study treatment.

System	Laboratory Value
Hematological*	
Hemoglobin (Hgb)	≥ 8 g/dL Transfusion of packed red blood cells or use of erythropoietin or analogs is permitted, if clinically appropriate, to achieve this threshold.
Absolute Neutrophil Count (ANC)	$\geq 1.0 \times 10^9/L$ Use of growth factors is permitted to fulfill this criterion if neutropenia is felt to be due to MM or due to prior therapy for MM.
Platelets	$\geq 50 \times 10^9/L$ if $< 50\%$ of bone marrow nucleated cells are plasma cells $\geq 30 \times 10^9/L$ if $\geq 50\%$ of BM nucleated cells are plasma cells. Platelet transfusions are permitted to reach entry criteria if thrombocytopenia is felt to be due to MM or due to prior therapy for MM.
Renal*	
Calculated creatinine clearance	Any GFR as long as not currently dialysis-dependent
Hepatic*	
Bilirubin	$\leq 2 \times$ upper limit of normal (ULN). Subjects with Gilbert's syndrome may be enrolled despite a total bilirubin level $> 2 \times$ ULN if their conjugated bilirubin is $< 2 \times$ ULN)
Aspartate aminotransferase (AST)	$\leq 3 \times$ ULN
Alanine aminotransferase (ALT)	$\leq 3 \times$ ULN

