4.2 Exclusion Criteria

All subjects meeting any of the listed exclusion criteria at baseline will be excluded from study participation.

- 4.2.1 Anti-myeloma treatment within 2 weeks of cycle 1 day 1
- 4.2.2 Subject is refractory to pomalidomide and/or known to be intolerant of pomalidomide at a dose of 3 mg or less.
- 4.2.3 Any monoclonal antibody therapy within the previous 28-days
- 4.2.4 Autologous stem cell transplantation within 12 weeks of day 1 of cycle 1
- 4.2.5 Subjects felt to not be candidates by treating physician for ANY systemic therapy due to excessive comorbidities, frailty, impaired performance status, or other severe limitations. Such limitations can be conceptualized generally as making subjects exceedingly high-risk for ANY systemic treatment. These limitations often stem from medical comorbidities unrelated to MM and they are hence unlikely to improve with MM therapy.
- 4.2.6 Light-chain (AL) amyloidosis. Subjects with secondary amyloidosis due to MM are eligible, providing amyloidosis is not felt to be a clinically significant issue (e.g., amyloid found incidentally on bone marrow core biopsy without evidence of amyloid-mediated organ compromise).
- 4.2.7 Myocardial infarction within 3 months prior to enrollment or has New York Heart Association (NYHA) Class III or IV heart failure (**Appendix N. New York Heart Association Classification of Cardiac Disease**), uncontrolled angina, severe uncontrolled ventricular arrhythmias, or electrocardiographic evidence of acute ischemia or active conduction system abnormalities.
- 4.2.8 Evidence of active bleeding requiring intervention within the last four weeks.
- 4.2.9 Current unstable liver or biliary disease per investigator assessment defined by the presence of ascites, encephalopathy, coagulopathy, hypoalbuminemia, esophageal or gastric varices, persistent jaundice, or cirrhosis. Note: Stable chronic liver disease (including Gilbert's syndrome or asymptomatic gallstones) or hepatobiliary involvement of malignancy is acceptable if patient otherwise meets entry criteria.
- 4.2.10 Any major surgery within the last four weeks

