5.7 Absolutely or Relatively Contraindicated Medications/Treatments

The following products and procedures are prohibited during the study:

- Any antineoplastic treatment with activity against MM, other than study drugs
- Radiation therapy except as approved by the study PI for symptom palliation.
- Short-course additional corticosteroids are permitted for the treatment of other medical problems. Longer-term additional steroids (> 2 weeks) should be discussed with study PI.
- Subjects taking concomitant therapies such as erythropoietin-stimulating agents or estrogen containing therapies may have an increased risk for thrombosis with concomitant administration of pomalidomide.

See Appendix A

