8.4 Assessment of Efficacy

Any subject who receives treatment on this protocol will be evaluable for efficacy. Subjects who are withdrawn from the protocol before receiving any study treatment will not be evaluated for efficacy and will be replaced.

To assess disease status, MM labs will be performed as a baseline prior to treatment and then as outlined in the Time and Events Table.

This study will use the Consensus Criteria for Response by the International Myeloma Working Group (IMWG) Appendix O. Response Criteria for Multiple Myeloma [51].

The primary endpoint of the study is overall response rate as defined as the percentage of subjects achieving a partial response or better (\geq PR) to study therapy at any time (per IMWG criteria provided in Appendix O. Response Criteria for Multiple Myeloma).

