13.15 Appendix O. Response Criteria for Multiple Myeloma

This study will use the Revised Uniform Response Criteria by the International Myeloma Working Group (IMWG) provided below [51].

Response Category*	Standard IMWG response criteria
sCR, stringent complete response	Complete response as defined below plus normal FLC ratio and absence of clonal cells in bone marrow biopsy by immunohistochemistry (κ/λ ratio $\leq 4:1$ or $\geq 1:2$ for κ and λ patients, respectively, after counting ≥ 100 plasma cells)
CR, complete response**	Negative immunofixation on the serum and urine and disappearance of any soft tissue plasmacytomas and $< 5\%$ plasma cells in bone marrow aspirates
VGPR, very good partial response**	Serum and urine M-protein detectable by immunofixation but not on electrophoresis or $\geq 90\%$ reduction in serum M-protein, plus urine M-protein level < 100 mg per 24 h
PR, partial response	$\geq 50\%$ reduction of serum M-protein plus reduction in 24 h urinary M-protein by $\geq 90\%$ or to < 200 mg per 24 h; If the serum and urine M-protein are unmeasurable, a $\geq 50\%$ decrease in the difference between involved and uninvolved FLC levels is required in place of the M-protein criteria; If serum and urine M-protein are unmeasurable, and serum-free light assay is also unmeasurable, $\geq 50\%$ reduction in plasma cells is required in place of M-protein, provided baseline bone marrow plasma-cell percentage was $\geq 30\%$. In addition to these criteria, if present at baseline, a $\geq 50\%$ reduction in the size (SPD)§§ of soft tissue plasmacytomas is also required
MR, minimal response	$\geq 25\%$ but $\leq 49\%$ reduction of serum M-protein and reduction in 24-h urine M-protein by 50–89%. In addition to the above listed criteria, if present at baseline, a $\geq 50\%$ reduction in the size (SPD)§§ of soft tissue plasmacytomas is also required
SD, stable disease	Not recommended for use as an indicator of response; stability of disease is best described by providing the time-to-progression estimates. Not meeting criteria for complete response, very good partial response, partial response, minimal response, or progressive disease

Response Category*	Standard IMWG response criteria

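### Baseline marrow and plasmacytoma scans may predate the end of prior therapy or radiotherapy, so earlier regression can count towards response in a subset of unknown size

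*Combined protocol and SAP*

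**What the plan says.** **Baseline windows (8.1, footnote 1).** For marrow: "Baseline bone marrow biopsy/aspirate should be obtained within 4 weeks prior starting treatment on cycle 1 day 1". For plasmacytoma imaging: "all imaging assessments should be performed within 21 days prior to day 1 of study treatment in cycle 1". For the rest, including screening M-protein and FLC: "All screening evaluations (except for pregnancy test) must be performed within 21 days prior to cycle 1 day 1 unless otherwise stipulated". M-protein and FLC are marked again at C1D1; marrow and plasmacytoma imaging are not.

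**Prior treatment.** Exclusion 4.2.1 is "Anti-myeloma treatment within 2 weeks of cycle 1 day 1". Exclusion 4.2.3 sets 28 days for monoclonal antibodies. Under 4.1.9 a subject who needs radiotherapy may be enrolled, but "initiation of study therapy should be deferred until the radiotherapy is completed and 14 days have elapsed". During the study, 5.7 prohibits "Radiation therapy except as approved by the study PI for symptom palliation".

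**Response.** Section 8.4 says that "MM labs will be performed as a baseline prior to treatment", without saying whether the screening or the C1D1 sample is the reference. In Appendix O, when serum M-protein, urine M-protein and FLC are all unmeasurable, a 50% "reduction in plasma cells is required in place of M-protein", given at least 30% plasma cells at baseline. Marrow results need no confirmation. A plasmacytoma present at baseline must also shrink by at least 50% (SPD) for MR or PR and must disappear for CR. Appendix O has no rule for irradiated lesions.

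**The concern.** The windows in which the baseline may be taken are longer than the washouts, and nothing puts the two in order. A compliant subject can have a baseline marrow or scan, then finish a previous regimen or a short course of radiotherapy, then start study treatment with less disease than the baseline shows. The on-study value is compared with the older, higher one, and the difference is credited to study therapy.

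Two groups are exposed. Marrow-only subjects have a PR that rests on one baseline marrow and one on-study marrow, with no pre-dose repeat that would reveal the change. Subjects with a plasmacytoma can have the SPD condition met by radiation given after the baseline scan. Section 4.1.9 expects some radiotherapy between enrolment and first dose, so that route is a realistic one.

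The primary endpoint is a single-arm ORR tested against a fixed 31%. There is no control arm in which misattributed responses would also appear.

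**Working it through.** **1. The plan's own figures (10.2).** Stop if 7 or fewer of 25 respond; reject the null if 21 or more of 49 respond. The exact rejection probability is the sum over x = 8 to 25 of P[Bin(25, p) = x] × P[Bin(24, p) ≥ 21 − x]. At p = 0.31 this gives 0.0522 and at p = 0.48 it gives 0.800. The stated 0.052 and 0.80 are reproduced.

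**2. Overlap: baseline window minus washout, in days.**

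| Baseline measure | Window | Washout | Overlap |
|---|---|---|---|
| Marrow vs non-antibody therapy or radiotherapy | 28 | 14 | 14 |
| Marrow vs monoclonal antibodies | 28 | 28 | 0 |
| Plasmacytoma imaging vs non-antibody therapy or radiotherapy | 21 | 14 | 7 |
| Screening M-protein/FLC vs non-antibody therapy or radiotherapy | 21 | 14 | 7 |
| C1D1 M-protein/FLC | at most 3 (visit window) | 14 | none |

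Counting the boundary day differently changes an entry by one day.

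**3. What each overlap can do under Appendix O.**
- *Marrow-only:* the plasma-cell reduction decides PR, is measured from the early baseline and is not confirmed.
- *Plasmacytoma:* the SPD reduction is required in addition to the M-protein, FLC or marrow criterion. Radiation cannot create a PR alone. It can complete one for a subject who meets the other criterion but whose lesion did not respond to study therapy.
- *Secretory:* a sample after washout exists but is not named as the reference. Near the 0.5 g/dL entry threshold the choice matters. With 0.6 g/dL at screening and 0.5 at C1D1, the PR cut-off is 0.30 or 0.25 g/dL.

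**4. Possible effect on the test (assumption).** The documents give no rates. Let f be the share of subjects whose response rests on a baseline taken before their last treatment, and q the share of their true non-responders who are miscounted. The null ORR becomes 0.31 + f × q × 0.69.

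| f | q | Points added | Type I error |
|---|---|---|---|
| 0 | – | 0 | 0.052 |
| 2% | 25% | 0.35 | 0.058 |
| 5% | 25% | 0.86 | 0.068 |
| 5% | 50% | 1.73 | 0.087 |

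Directly, 0.5 points (p = 0.315) gives 0.061, 1 point (0.32) gives 0.071 and 2 points (0.33) gives 0.094. Adding 2 points needs f × q = 0.02 / 0.69 = 2.9%, for example f = 5.8% (about 3 of 49 subjects) with q = 50%.

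**The case against.** The strongest reply is that eligibility makes carry-over unlikely. Section 4.1.3 requires relapsed disease, or disease relapsed and refractory to the last line, and a subject regressing on the regimen just finished fits neither well. Section 11.3 requires eligibility to be maintained until treatment starts. Consider a marrow-only subject who falls from 45% to 20% plasma cells before C1D1: the fall is 25/45 = 56%, enough for PR, but 20% is below the 30% entry floor. The 20% would also have to hold on ineffective therapy until the next marrow, which for non-secretory disease is scheduled every 12 weeks. This stands as a reason to expect few cases. It does not close the gap, because no C1D1 marrow is scheduled to show the fall, and 4.1.9 allows radiotherapy after enrolment whatever the response to the last line.

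Other limits also stand. Antibody therapy has no overlap with the marrow window. Most subjects are likely to be assessed on M-protein or FLC, which is repeated at C1D1. On-study radiotherapy needs PI approval. In a subject progressing untreated through screening, an early baseline is too low and makes PR harder to reach; that error runs the other way, in different subjects.

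A reader might infer that regression from earlier therapy is routinely counted as response, or that type I error is as high as 0.155. The first does not follow: the text permits the miscount in a subset and says nothing on its size. The second needs 4 added points (p = 0.35), so f × q = 0.04 / 0.69 = 5.8%, for example about 12% of all subjects on such a baseline with half their non-responders miscounted. Nothing in the documents supports that.

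**Conclusion.** The gap is real but narrow. For marrow and plasmacytoma imaging, the plan lets the response baseline precede the end of non-antibody therapy or radiotherapy by up to 14 and 7 days. In the affected subjects the error favours response. For secretory subjects the gap is only the unnamed reference sample.

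The size cannot be derived from the documents. The range of about 0.06 to 0.09 for type I error rests entirely on the assumed 0.5 to 2 added points. If the baseline follows the last prior treatment, this carry-over is removed and the stated design is unchanged: 49 subjects, type I error 0.052, power 0.80. The change is worth making because it costs little and protects an uncontrolled primary endpoint.

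**What to change.** 1. **Section 8.4:** define baseline M-protein and FLC as the last value before the first dose, normally C1D1.
2. **Section 8.1, footnote 1:** schedule the required baseline marrow and plasmacytoma imaging, within their existing windows, after the last dose of prior anti-myeloma therapy and the last radiotherapy fraction. Do not mandate a repeat biopsy. Where the only marrow predates that treatment, flag the subject and report, as a sensitivity analysis, the ORR with that subject counted as a non-responder. Each response reclassified this way lowers the ORR by 1/49, about 2 points.
3. **Appendix O:** state that a plasmacytoma irradiated after its baseline measurement, including under 5.7, cannot supply the SPD reduction for MR or PR or the disappearance condition for CR. The VGPR row has no plasmacytoma condition and needs no change.

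The cost is wording in three places, slightly tighter screening scheduling and possibly a few fewer counted responses. A blanket repeat-marrow rule would not be cheap: a frail subject whose relapse marrow came before the end of prior treatment would need a second biopsy. That is why flagging is preferred.
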